## **Exclusion Criteria**

- Pregnant patients or patients planning to become pregnant during the time of the study.
- Patients with a history of use of hydroquinone, kojic acid, tretinoin, adapalene, tazarotene or azaleic acid in the previous 3 months
- 5.0 Enrollment/Randomization

Patients presenting to the dermatology clinic with PIH secondary to acne vulgaris and are interested in a potential treatment will be considered as candidates for participation. If their treating physician in clinic determines they are eligible, they will be referred to the PI or sub-PI for screening and consent. The study design and consent will be explained, their expectations for participation will be discussed, and any questions will be addressed. The patient will then have the choice to participate or decline participation in the study. Block randomization will be utilized to determine which side will be the treatment side.

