#### 6.0 Study Procedures

Patients with bilateral disease will be chosen to participate in the study. Patients will be advised to discontinue any other facial cleansers or products prior to beginning treatment. One side of the patient will be chosen as the treatment side, and the other as an intrinsic control. Each day, the participant will wash their face in the morning with a standard cleanser, dry their face, then apply the medication to the treatment side of their face only to areas of unwanted dark spots. The patient will then apply the vehicle to the other side of their face only to the areas of unwanted dark spots. The patient will wait 30 minutes, and then apply a standardized sunscreen SPF 30+ to entire face. Each night, the patient will again wash their face. Patients will participate in a follow-up clinic visit 4 weeks, 8 weeks and 12 weeks after beginning treatment. At each visit, photographs will be taken of their face to monitor progression and to serve as a comparison to the control side. The postacne hyperpigmentation index, a validated system for evaluating hyperpigmentation due to acne vulgaris, will be used to monitor the progression of facial lesions. At week 0 and 12, the patients will take a survey to determine the impact that their facial spots have on their quality of life.

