## 9.0 Statistical Considerations

We will attempt to demonstrate clinical improvement of the postinflammatory hyperpigmentation by decreasing the size, intensity, and number of the facial lesions by comparing the treatment side to the control side of the face.

Patients will be evaluated prior to treatment, and at each follow-up visit both 4 weeks, 8 weeks and 12 weeks post-treatment using the Postacne Hyperpigmentation Index (PAHPI). The scoring system is as follows:

Weighted score (S)		Median lesion size
2		<3 mm
4		3-6 mm
6		7-10 mm
8		>10 mm
Weighted score (I)		Median lesion intensity
3	Slightly darker than surrounding skin	
6	Moderately darker than surrounding skin	
9	Significantly darker than surrounding skin	
Weighted score (N)		No. of lesions
1		1-15
2		16-30
3		31-45
4		46-60
5		>60

 Table I. Scoring the postacne hyperpigmentation index

Total postacne hyperpigmentation index = S + I + N; score range: 6-22.

Using power analysis to determine sample size:

In the study by Kim et al, they demonstrated a significant decrease in melasma, another disorder of facial hyperpigmentation, using topical tranexamic acid. They demonstrated a significant decrease in the melasma area and severity index of approximately 33% with a sample size of 23 patients. For our study, a sample size of 25 patients is sufficient to detect a clinically important difference of 30% between treatment and control sides of the face using a two-tailed z-test of proportions between two groups of 80% power and a p-value of 0.05.

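### Active product is applied before vehicle every day with no step against transfer between sides, so the split-face difference may be diluted toward zero

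*Combined protocol and SAP*

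**What the plan says.** The trial is a split-face comparison. Section 6.0 (Study Procedures) states: "One side of the patient will be chosen as the treatment side, and the other as an intrinsic control". It then sets out one daily sequence:

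1. The face is washed: "Each day, the participant will wash their face in the morning with a standard cleanser".
2. After drying, the participant is to "then apply the medication to the treatment side of their face only to areas of unwanted dark spots".
3. The vehicle follows: "The patient will then apply the vehicle to the other side of their face only to the areas of unwanted dark spots".
4. Sunscreen comes last: "The patient will wait 30 minutes, and then apply a standardized sunscreen SPF 30+ to entire face".

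No hand washing, gloves, separate applicators or other barrier appears between steps 2 and 3, before step 4, or elsewhere in the supplied text. The means of application (fingers, pad, dropper) is not stated.

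Section 5.0 (Enrollment/Randomization) says what is allocated at random: "Block randomization will be utilized to determine which side will be the treatment side". The order of application is not randomised.

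Section 9.0 (Statistical Considerations) bases efficacy on the treatment side against the control side. It plans 25 patients to detect a "difference of 30% between treatment and control sides of the face" with a two-tailed z-test of proportions, 80% power and a 0.05 significance level. It makes no allowance for transfer between sides.

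**The concern.** In a split-face trial, treatment and control sit a few centimetres apart and the participant applies both. The order here follows the product, not the side. Whichever side is allocated, the active product comes first and the vehicle second. Any transfer by hand between these two steps therefore runs from active to control in every participant, and randomising the side does not average it out.

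If the product works, exposure of the control side improves that side and shrinks the contrast. Nothing in the plan measures active product on the control side, and there is no separate group of patients who receive vehicle only, so the analysis could not adjust for it. At one application a day, the 12-week treatment period gives 12 × 7 = 84 occasions per participant on which transfer could occur.

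At stake are an underestimated effect and a loss of power. If both sides improved, a small side-to-side difference would also be harder to interpret.

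**Working it through.** **Inputs from the documents.** 25 patients; difference of 30% between sides; two-sided test at 0.05; 80% power; z-test of two proportions (all Section 9.0). Active first and vehicle second, daily (Section 6.0). Side randomised, order not (Section 5.0).

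**Inputs that are not in the documents.** The share *f* of the treatment effect that reaches the control side; the control-side proportion; the SD of the within-patient difference. These are assumptions below. Note that *f* is a share of effect, not of residue.

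**The plan's own figure.** Reading 30% as an absolute difference and using the pooled-variance formula

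n = [1.96·√(2p̄(1−p̄)) + 0.842·√(p₁(1−p₁) + p₂(1−p₂))]² / (p₂−p₁)²,

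the number per group is 22 for 0% vs 30%, 25 for 3% vs 33%, 27 for 5% vs 35%, 32 for 10% vs 40% and 43 for 35% vs 65%. With no control proportion stated, 25 cannot be uniquely reproduced. It fits only when that proportion is a few percent (or in the mirror case near 100%). The dilution is therefore shown in two ways.

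**A. Paired t-test, 25 pairs.** A standardised difference of 0.584 gives 80% power (noncentral t, 24 degrees of freedom, noncentrality 0.584·√25 = 2.92, critical value 2.064). Carry-over multiplies the difference by (1 − *f*).

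| *f* | Standardised difference | Noncentrality | Power | Pairs needed for 80% |
|---|---|---|---|---|
| 0 | 0.584 | 2.92 | 80.0% | 25 |
| 5% | 0.555 | 2.77 | 75.9% | 28 |
| 10% | 0.526 | 2.63 | 71.3% | 31 |
| 20% | 0.467 | 2.34 | 61.1% | 38 |
| 30% | 0.409 | 2.04 | 50.1% | 49 |

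**B. The plan's z-test of proportions, 25 per side.** The assumed starting point is 2% (control) vs 32% (treated). With carry-over the control proportion becomes 2% + *f* × 30%, and

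power = Φ{[d·√25 − 1.96·√(2p̄(1−p̄))] / √(p₁(1−p₁) + p₂(1−p₂))}.

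| *f* | Control | Treated | Difference d | Power |
|---|---|---|---|---|
| 0 | 2% | 32% | 0.30 | 83% |
| 10% | 5% | 32% | 0.27 | 70% |
| 20% | 8% | 32% | 0.24 | 57% |
| 30% | 11% | 32% | 0.21 | 44% |

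Example at *f* = 10%: p̄ = 0.185; (1.35 − 1.96 × 0.549) / 0.515 = 0.53; Φ(0.53) = 0.70.

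From a different assumed start, 20% vs 50%, power is 61% with no carry-over and about 51%, 41% and 33% at 10%, 20% and 30%. The direction and rough scale of the loss are the same in each model; the absolute level depends on the assumed inputs.

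**The case against.** The strongest reply is that the protocol is silent; it does not prescribe contamination. Section 6.0 does not say how either product is put on, and transfer needs a shared finger or applicator. Both products go only on dark spots. Consent pages were removed and participant instructions were not supplied, so a hand-cleaning instruction may exist elsewhere. Any bias is toward the null, so it could not create a false claim of benefit. The carry-over shares have no source in the documents. The PAHPI is scored in bands (size in steps of 2, intensity in steps of 3), so slight exposure need not move it in proportion.

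Much of this stands, and it rules out several stronger readings that a reader might infer:

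- **That active product reaches the control side in every participant at every application.** The text supports only that it may.
- **That power will fall by the amounts shown.** The figures are illustrations. The paired t-test is not the plan's test, and the 2% vs 32% start is assumed.
- **That a null result could not be told apart from carry-over.** PAHPI is scored before treatment and at weeks 4, 8 and 12. If neither side improved, carry-over would not be a credible explanation. The ambiguity arises when both sides improve, and then natural fading and sunscreen on both sides are rival explanations.
- **That the step between the two products is the only route.** The whole-face sunscreen is a second possible one, and hand cleaning between the two products alone would not close it.

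What the reply does not answer is that Section 6.0 spells out washing, drying, a 30-minute wait and sunscreen, yet has no step to keep the sides apart. Participants who clean their hands unprompted would do so unevenly.

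**Conclusion.** The concern holds as a possibility that the written procedure leaves open. The order is fixed as active then vehicle for everyone, only the side is randomised, and the contrast at risk is the one on which efficacy rests. The direction of the bias is clear if the product has an effect: toward zero, with loss of power. Its size is unknown. At an assumed 10% to 30% share of effect carried over, power at 25 patients would be roughly 71% to 50% instead of 80% (paired t-test), or 70% to 44% instead of 83% (z-test at an assumed 2% vs 32%).

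The conclusion assumes that the same fingers or applicator may be used on both sides and that no instruction outside the supplied text prevents it. It is a cheap improvement worth making, not evidence that the trial would fail. It is best made before participants start, because dilution cannot be removed in the analysis afterwards.

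**What to change.** In Section 6.0, and in the participant instructions, add a contamination-control step:

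- Between the two applications, hands are washed and dried, or a separate labelled applicator is used for each side.
- Hands are clean before the whole-face sunscreen, and the sunscreen is spread on each side separately.

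Product, amount, frequency and area stay unchanged. If such an instruction already exists in participant material, Section 6.0 should state it.

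The cost is a sentence or two in the protocol and in the instructions, and about a minute more per day for the participant. No change to the sample size or analysis follows from this point alone.

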#### 7.0 Risks

Risks of topical TA include skin erythema and irritation. There may also be risks involved with this with this study that are unknown to the researcher at this time.

#### 8.0 Study Withdrawal/Discontinuation

The participant is free to withdraw from the study at any time. He/she should inform the primary investigator or any co-investigator.

## 9.0 Statistical Considerations

We will attempt to demonstrate clinical improvement of the postinflammatory hyperpigmentation by decreasing the size, intensity, and number of the facial lesions by comparing the treatment side to the control side of the face.

Patients will be evaluated prior to treatment, and at each follow-up visit both 4 weeks, 8 weeks and 12 weeks post-treatment using the Postacne Hyperpigmentation Index (PAHPI). The scoring system is as follows:

Weighted score (S)		Median lesion size
2		<3 mm
4		3-6 mm
6		7-10 mm
8		>10 mm
Weighted score (I)		Median lesion intensity
3	Slightly darker than surrounding skin	
6	Moderately darker than surrounding skin	
9	Significantly darker than surrounding skin	
Weighted score (N)		No. of lesions
1		1-15
2		16-30
3		31-45
4		46-60
5		>60

 Table I. Scoring the postacne hyperpigmentation index

Total postacne hyperpigmentation index = S + I + N; score range: 6-22.

Using power analysis to determine sample size:

In the study by Kim et al, they demonstrated a significant decrease in melasma, another disorder of facial hyperpigmentation, using topical tranexamic acid. They demonstrated a significant decrease in the melasma area and severity index of approximately 33% with a sample size of 23 patients. For our study, a sample size of 25 patients is sufficient to detect a clinically important difference of 30% between treatment and control sides of the face using a two-tailed z-test of proportions between two groups of 80% power and a p-value of 0.05.

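### Section 9.0 ties its only test and its 0.05 to no measure or visit, and that two-group z-test of proportions does not fit a PAHPI score compared between two sides of the same face

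*Combined protocol and SAP*

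**What the plan says.** Section 9.0 is the whole statistical plan. Its aim is to show improvement "by decreasing the size, intensity, and number of the facial lesions by comparing the treatment side to the control side of the face". It then tabulates the Postacne Hyperpigmentation Index, adds the three items into one number ("Total postacne hyperpigmentation index = S + I + N", range 6-22), and has it scored before treatment and at weeks 4, 8 and 12. Section 6.0 says that the index "will be used to monitor the progression of facial lesions", and adds a quality-of-life measure: "At week 0 and 12, the patients will take a survey to determine the impact that their facial spots have".

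A test and a significance level appear once, in the sample-size sentence. It says that 25 patients suffice for "a clinically important difference of 30% between treatment and control sides of the face" when "using a two-tailed z-test of proportions between two groups of 80% power and a p-value of 0.05". Nothing defines what makes a side a success, so the proportion being tested is not identified. No section names a primary measure or visit, ranks the survey, or says how results across visits are to be combined.

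**The concern.** There are two linked gaps.

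1. The 0.05 is attached to nothing. Three visits, one total, three items and a survey are all available, and the plan does not say which result decides whether the treatment worked. The choice could be made with the data in hand. If any favourable visit were allowed to count, the chance of a false claim of benefit would rise above that of a single test.

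2. The one named test does not fit the data. It compares proportions in two independent groups. The data are an ordered score on two sides of the same face, so the observations are paired and no binary outcome exists. The sample-size sentence therefore cannot serve as an implied definition of the primary analysis, and the stated 80% power is power for a comparison that nobody could carry out as written.

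**Working it through.** **Inputs from the documents (Section 9.0):** 25 patients, each giving one treated and one control side; two-sided 0.05, which is 0.025 in the direction of benefit; 80% power; a 30% difference; three post-baseline visits. **Not in the documents, so assumed:** correlation between visits, correlation between sides, responder share, standard deviation of PAHPI, and any rule that one significant visit is enough.

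**1. The plan's own figure.** For two independent proportions p1 and p2 = p1 + 0.30, with mean p, the number per side is

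n = [1.96 × √(2p(1−p)) + 0.842 × √(p1(1−p1) + p2(1−p2))]² / 0.30²

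At 3% vs 33%: [1.96 × √0.2952 + 0.842 × √0.2502]² / 0.09 = 24.5, so 25.

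| Control vs treated | n per side | Power at 25 per side |
|---|---|---|
| 0% vs 30% | 22 | 87% |
| 3% vs 33% | 25 | 81% |
| 5% vs 35% | 27 | 77% |
| 10% vs 40% | 32 | 70% |
| 35% vs 65% | 43 | 57% |

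The plan gives no control proportion. With this two-sided pooled formula, 25 is reached only for a control proportion of about 3% or a few points around it (or the mirror image near 100%).

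**2. Any one of three visits, paired t-tests on total PAHPI.** With no true effect and 25 pairs, false benefit is the chance that at least one of three correlated statistics passes the upper critical value. With independent visits this is 1 − 0.975³ = 7.3%. With perfect correlation it is 2.5%. Between these limits, by simulation with t on 24 degrees of freedom:

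| Assumed visit correlation | False benefit |
|---|---|
| 0.5 | 6.3-6.4% |
| 0.8 | 5.0% |
| 0.9 | 4.2-4.3% |

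The trivariate normal calculation agrees: 6.3% at 0.5 and 4.9% at 0.8.

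**3. The same rule with the plan's z-test.** Pooled two-group z-test, 25 per side, no true effect, responders simulated by cutting a latent normal score, responder share 30-50%, visit correlation 0.5-0.8:

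| Assumed between-side correlation | One visit | Any of three visits |
|---|---|---|
| 0 | about 3% | about 6-8% |
| 0.5 | about 1% | about 3% |
| 0.7 | about 0.5% | about 1% |

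Counting any visit multiplies the single-visit rate by roughly 2.3 to 3.1. The absolute level falls as the sides become more alike, because the test ignores the pairing and overstates the standard error of the difference.

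**4. What 25 pairs can detect.** For a paired t-test at two-sided 0.05 and 80% power, the normal approximation gives (1.96 + 0.842)/√25 = 0.56 SD of the within-patient difference; the noncentral t gives 0.584. In points this is 0.584 × SD × √(2(1−r)), where SD is the per-side standard deviation and r the side correlation:

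- SD 2, r 0.7: 0.90 points
- SD 3, r 0.5: 1.75 points
- SD 4, r 0.3: 2.76 points

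These are before any gain from baseline adjustment, and every SD and r is an assumption.

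**The case against.** The strongest reply is that the ambiguity is narrow. PAHPI is the only scored efficacy instrument, its items are explicitly summed, week 12 is the last visit, and Section 6.0 describes the index as a monitoring tool, which suits weeks 4 and 8 as interim readings. Most statisticians would take total PAHPI at week 12 as primary. That stands, and it limits the severity. But a natural reading does not bind the analyst, and it does not say how the comparison is to be tested, since the one test named cannot be applied to that score.

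The second reply is that the 5-6% comes from a rule and a test absent from the plan. That also stands. A reader might infer that this trial's false-positive rate is 5-6%. The documents do not support this: they state no any-visit rule, no paired test and no correlations, and under the z-test they do name, even the any-visit rule gives about 3% at side correlation 0.5 and about 1% at 0.7.

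A reader might also take size, intensity and number as three rival endpoints, or as three hurdles that must all be cleared. The wording of the aim gives that little support, because the same section adds them into one total.

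**Conclusion.** The point holds as an omission combined with a test that does not match the design. That no primary measure, primary visit or multiplicity rule is stated is certain, as is the lack of a responder definition for the z-test. The documents do not show that the sponsor intends to choose among results; they only leave this possible.

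The size of any inflation is conditional. Under an any-visit rule it is about 5-6% false benefit against 2.5% with paired t-tests at visit correlation 0.5-0.8, and anywhere from about 1% to about 8% with the plan's z-test over side correlations of 0.7 down to 0. The statement that 25 patients give 80% power can be reproduced with the stated test only for a control proportion close to 3% (or the mirror near 100%), which the plan does not state. This should be corrected, but the design remains analysable with the data already planned.

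**What to change.** Before analysis, replace the two-group z-test with one named primary comparison: the within-patient treated-minus-vehicle difference in total PAHPI, scored on each side, 12 weeks after beginning treatment, adjusted for the baseline scores and tested at two-sided 0.05. Declare weeks 4 and 8, the separate S, I and N items, and the survey secondary, and report the items with confidence intervals.

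Restate the power sentence for that comparison: 25 pairs give 80% power for a mean side difference of 0.58 SD of the within-patient difference. State the assumed SD and side correlation openly, and say whether the resulting difference in points is clinically worthwhile on this score.

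The cost is a few sentences and one recalculation with new assumed inputs; no extra patients, visits or procedures are needed. The downside is that an isolated early-visit or single-item result can no longer be called a positive trial.

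### The stated 80% power with 25 patients has no stated control-side rate and, on the plan's own z-test, holds only if that rate is about 3% or less

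*Combined protocol and SAP*

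**What the plan says.** The sample-size text in section 9.0 (Statistical Considerations) first cites a study of topical tranexamic acid in melasma: "They demonstrated a significant decrease in the melasma area and severity index of approximately 33% with a sample size of 23 patients". No comparator, SD or responder rate is given for it. The next sentence states that "a sample size of 25 patients is sufficient to detect a clinically important difference of 30% between treatment and control sides of the face". The method it names for this calculation is a "two-tailed z-test of proportions between two groups of 80% power and a p-value of 0.05". It gives no expected rate for either side.

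Section 6.0 (Study Procedures) describes a split-face design: "One side of the patient will be chosen as the treatment side, and the other as an intrinsic control". The control side is not untreated: "The patient will then apply the vehicle to the other side of their face only to the areas of unwanted dark spots". The whole face is washed with a standard cleanser, and patients "apply a standardized sunscreen SPF 30+ to entire face". The outcome is the postacne hyperpigmentation index (PAHPI, range 6 to 22), assessed at weeks 4, 8 and 12.

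**The concern.** For a test of two proportions, a difference alone does not determine power. The variance depends on the two rates, so a 30-point difference needs different numbers of patients at different control-side rates. Without that rate, the 80% cannot be interpreted.

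The cited 33% does not supply it. As described, it is a decrease in treated patients, whereas this trial compares a treated side with a vehicle side of the same face. If the 33% stands for the treated side, a 30-point difference leaves 33 − 30 = 3 points for the vehicle side. Any further response there cuts the difference or, if the treated side rises equally, raises the variance. Both lower power on the stated test.

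At stake is how a null result is read. Anyone relying on the stated 80% could take non-significance as evidence of no effect, when that figure assumed a nearly inert control side.

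**Working it through.** **Inputs.** From section 9.0: difference 0.30, two-sided alpha 0.05 (z = 1.960), power 80% (z = 0.8416), 25 patients. From section 6.0: both sides of each face are used, so 25 observations per side. The vehicle-side rate is not in the documents; every value used for it below is an assumption.

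**Formulas** (z-test of two proportions, pooled variance, equal numbers, no continuity correction). With vehicle-side rate c, treated-side rate t, m = (c + t)/2, A = √[2m(1 − m)] and B = √[c(1 − c) + t(1 − t)]:

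- n per side = (1.960·A + 0.8416·B)² / (t − c)²
- power = Φ{[(t − c)·√n − 1.960·A] / B}

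**Reproducing the plan's figure.** Take t = 0.33 and c = 0.03, so m = 0.18:

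- A = √(2 × 0.18 × 0.82) = 0.5433
- B = √(0.0291 + 0.2211) = 0.5002
- n = (1.0649 + 0.4210)² / 0.09 = 24.5, rounded up to 25
- power at 25 = Φ[(0.30 × 5 − 1.0649)/0.5002] = Φ(0.870) = 80.8%

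At the same 30-point difference, n is 24 for 2% vs 32% and 26 for 4% vs 34%. Among whole-percent rates, only 3% vs 33% and its mirror image, 67% vs 97%, return 25.

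**Other forms of the test.** At 33% vs 3%, the unpooled formula gives 22, arcsine 21 and the continuity-corrected formula 31. Unpooled and arcsine both need 24 at 5% vs 35%, and 29 and 30 at 10% vs 40%, so the limiting rate moves only slightly above 5%. With the continuity correction, even 0% vs 30% needs 28.

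**Varying the vehicle-side rate, 25 per side:**

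| Vehicle-side rate | Power, 30-point difference kept | Power, treated side held at 33% | n per side for 80%, treated side at 33% |
|---|---|---|---|
| 3% | 80.8% (3 vs 33) | 80.8% | 25 |
| 5% | 77% (5 vs 35) | 73% | 30 |
| 10% | 70% (10 vs 40) | 51% | 49 |
| 15% | 65% (15 vs 45) | 32% | 88 |
| 20% | 61% (20 vs 50) | 18% | 180 |

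Worked example at 10%:

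- Difference kept (10 vs 40): A = √0.375 = 0.6124, B = √0.33 = 0.5745; power = Φ[(1.5 − 1.2003)/0.5745] = Φ(0.522) = 70%.
- Treated side at 33%: A = 0.5810, B = 0.5578; power = Φ[(1.15 − 1.1387)/0.5578] = Φ(0.020) = 51%.

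**Paired continuous analysis.** A paired t-test on the side-to-side difference with n = 25 depends on its SD, which the documents do not give. For 30 points, power is 80% at SD 51.4. For 23 points (33 − 10), it is 96% at SD 30, 79% at SD 40 and 60% at SD 50. These SDs are illustrative assumptions.

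**The case against.** The strongest reply is that section 9.0 calls 30% clinically important and never says it was derived from the 33%. Powering for an importance threshold is legitimate, and the calculation is then conditional on that difference whatever the vehicle side does. The first part stands: derivation from the 33% is an inference, supported by the match at 33% vs 3% but not proved by it. The second part fails for this test. With the 30 points kept, power still falls from 80.8% to 61% as the vehicle-side rate rises from 3% to 20%.

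It can also be said that no vehicle-side response is documented. That stands. The plan gives no such figure, and section 1.0 says the discoloration may last years, so substantial spontaneous fading cannot be assumed. Nor do the documents say how much the cleanser or sunscreen would contribute. The table shows sensitivity, not an expected loss.

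A reader might infer that 25 patients would be too few even with a correct paired analysis. The documents do not support this. The cited 33% is a percentage change in an index, not a responder proportion, and a z-test between two groups does not describe a paired PAHPI score. True power depends on the missing SD and could be above or below 80%.

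**Conclusion.** The concern holds as a statement about the plan's own calculation. On the pooled two-tailed z-test with 25 per side, 80% power for a 30-point difference requires a vehicle-side rate of about 3% or less, or the mirror case with the treated side at about 97% or more. The plan neither states nor justifies such a rate, and its one cited result does not provide it. At an assumed vehicle-side rate of 10%, power is 70% with the 30 points kept and 51% with the treated side at 33%.

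These figures rest on reading the outcome as a proportion, as the named test requires, and on assumed vehicle-side rates. They do not show that the trial as run would be underpowered, or that the 30% was taken from the 33%.

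**What to change.** Reword the sample-size sentence in section 9.0 to:

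- define the planning difference as treated side minus vehicle side at week 12;
- state the vehicle-side rate assumed, with its reason;
- say that, on the stated test, 80% power with 25 patients holds only at a vehicle-side rate of about 3% or less (mirror case aside);
- give power for vehicle-side rates of 5% to 20%, as in the table.

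If 30% is meant as an importance threshold, say so, give the reason, and stop resting it on the 33% decrease. Make no claim in either direction about power under a paired analysis unless an SD for the side-to-side PAHPI difference is supplied.

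The cost is a rewritten paragraph and a less favourable stated power. No extra patients are needed.

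### The 80% power claim for 25 patients rests on a two-group z-test of proportions that fits neither the PAHPI score nor the split-face design, and its inputs are not stated.

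*Combined protocol and SAP*

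**What the plan says.** The sample-size justification is the last paragraph of Section 9.0. It cites a melasma study that found "a significant decrease in the melasma area and severity index of approximately 33% with a sample size of 23 patients", then concludes that "a sample size of 25 patients is sufficient to detect a clinically important difference of 30% between treatment and control sides of the face". The method behind that conclusion is named only at the end of the sentence: "using a two-tailed z-test of proportions between two groups of 80% power and a p-value of 0.05". No other statistical test is named in the document.

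The same section defines the outcome as a sum of three weighted components: "Total postacne hyperpigmentation index = S + I + N; score range: 6-22".

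The design is within-patient. Section 5.0 (Enrollment/Randomization) states: "Block randomization will be utilized to determine which side will be the treatment side". Section 6.0 adds: "One side of the patient will be chosen as the treatment side, and the other as an intrinsic control". Section 8.0 allows withdrawal ("The participant is free to withdraw from the study at any time"), and no allowance for dropout is given.

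**The concern.** The named test compares the proportions of responders in two independent groups. This trial has an ordered score with no response threshold, measured on two sides of one face. The test therefore mismatches both the type of outcome and the dependence between the arms.

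A sample size for two proportions also needs both rates, because the variance depends on them. A difference of 30% alone does not fix the sample size, and the plan does not say whether 30% means percentage points of responders or a relative difference in score. The cited 33% fall cannot fill the gap: it is a reduction in an index, neither a responder rate nor a difference between treated and vehicle sides.

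This sentence is the trial's only sample-size justification. If the result is not significant, a reader could take it as excluding an important difference with 80% power, which the plan has not shown. The PAHPI difference that 25 pairs can detect is never stated. Since no other test is named, the independent-groups z-test could also be taken as the planned analysis.

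**Working it through.** **Inputs from Section 9.0.** 25 patients, hence 25 treated and 25 vehicle sides; two-sided 5% (z = 1.96); 80% power (z = 0.8416); difference d = 0.30, read here as percentage points of responders. The side rates are not given, so the vehicle rate p1 is varied, with p2 = p1 + 0.30 and p̄ = (p1 + p2)/2.

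**1. Can 25 be reproduced?** Pooled formula, sides treated as independent:

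n per side = [1.96·√(2p̄(1−p̄)) + 0.8416·√(p1(1−p1) + p2(1−p2))]² / 0.30²

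At 3% v 33%: p̄ = 0.18, and [1.96·√0.2952 + 0.8416·√0.2502]² / 0.09 = (1.065 + 0.421)² / 0.09 = 24.5, which rounds up to 25.

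So 25 would follow if the 33% index fall had been entered as a treated-side responder rate and 30 points subtracted. This is an inference, because the plan shows no derivation. If it is right, the arithmetic is sound but the input is not a proportion.

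**2. Power at 25 per side for other vehicle rates.**

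Pooled power = Φ{[0.30·√25 − 1.96·√(2p̄(1−p̄))] / √(p1(1−p1) + p2(1−p2))}

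For example, at 35% v 65%: Φ[(1.5 − 1.386)/0.675] = Φ(0.169) = 0.567.

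The formula is an approximation, so the test was also enumerated over all outcomes of two binomials of 25. This was done once with the usual critical value of 1.96 (true size up to 6.5%) and once with the critical value raised to 2.0395 (true size at most 4.6%).

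| Vehicle v treated | n per side (pooled) | Power, pooled | Power, enumerated | Power, enumerated, size-controlled |
|---|---|---|---|---|
| 3% v 33% | 24.5 | 0.808 | 0.875 | 0.829 |
| 10% v 40% | 31.5 | 0.699 | 0.734 | 0.690 |
| 20% v 50% | 38.5 | 0.609 | 0.638 | 0.606 |
| 35% v 65% | 42.4 | 0.567 | 0.622 | 0.522 |

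The results are symmetric about 35% v 65%. Vehicle rates at which power is at least 80%:

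- pooled: up to 3.4% or from 66.6%
- enumerated: up to 6.2% or from 63.8%
- size-controlled: up to 4.1% or from 65.9%

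Over an assumed vehicle range of 10% to 60%, power is 57–70%, 62–73% and 52–69% respectively.

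**3. The same difference with a paired test of proportions (McNemar).** Let ψ be the share of patients whose two sides differ in response. With a 30-point difference, ψ cannot be below 0.30.

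Closed formula: power = Φ{[0.30·√25 − 1.96·√ψ] / √(ψ − 0.09)}

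| ψ | Closed formula | Exact binomial | Enumerated, uncorrected |
|---|---|---|---|
| 0.30 | 0.824 | 0.807 | 0.967 |
| 0.35 | 0.748 | 0.690 | 0.812 |
| 0.40 | 0.680 | 0.602 | 0.709 |

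Power equals 80% at ψ = 0.315, 0.302 and 0.355 respectively. Pairing can therefore support 25 patients, but only near the minimum discordance, and the plan states no discordance.

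**4. What 25 pairs detect on the score.** Paired t-test, two-sided 5%, 80% power, noncentral t: a mean difference of 0.584 SD of the within-patient differences with 25 pairs, 0.626 SD with 22 and 0.660 SD with 20. The 22 and 20 completers are assumptions (12% and 20% loss).

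To illustrate in PAHPI points, assume an SD of 3 points per side and a within-patient correlation ρ. The SD of the differences is 3·√(2(1−ρ)), so the detectable difference is 0.584 times that: 2.48 points at ρ = 0, 1.75 at ρ = 0.5 and 1.11 at ρ = 0.8. Neither the SD nor ρ is in the plan.

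**The case against.** The strongest reply is that 25 may well be enough. If the sides are positively correlated, an independent-groups calculation overstates the patients needed for a paired comparison, so the mismatch could be conservative. That stands, and it is why this point does not call the trial underpowered. It does not rescue the sentence, which asserts a specific power without the inputs that would make it true.

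Second, 30% may have been meant as a relative difference in score, since the preceding sentence reports a percentage fall in an index. That is a fair reading. The responder-rate power figures would then not apply, but a z-test of proportions would not apply either, and an SD would be needed that the plan does not give.

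Third, the 10% to 60% vehicle range is the reviewer's choice and leaves out both regions where 80% is reached. Section 1.0 describes discoloration that can persist for years, so a very low vehicle response is arguable; but both sides also receive sunscreen, and the documents do not settle the rate. The figures of 52% to 73% are conditional illustrations, not the trial's likely power.

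Fourth, the 3% v 33% reconstruction is not unique: 67% v 97% gives the same number by symmetry. It remains an inference, and the conclusion does not depend on it.

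Finally, a detectable difference in SD units still has to be converted to PAHPI points with an assumed SD, and it needs a named visit. Both limits are accepted and carried into the fix.

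**Conclusion.** The concern holds. The plan's only power statement uses a test that matches neither the outcome nor the design, and its missing inputs mean it cannot be verified. On a percentage-point reading with independent sides, 80% power holds only at vehicle rates up to about 3% or from about 67% by the pooled formula, and only up to about 6% or from about 64% on the most favorable calculation. With a paired test of proportions, it requires discordance no higher than about 30% to 36%, depending on the version of the test. The plan states none of these conditions.

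The mismatch of test, outcome and design does not depend on any assumed rate. This is a must-fix because the sentence is wrong as written, not merely short of detail. It is not evidence that 25 patients are too few to compare PAHPI scores between sides.

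**What to change.** Keep 25 patients. In Section 9.0, remove the 33% index fall as support for a difference in proportions, and replace the z-test statement with a paired one. Suggested wording:

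*With 25 patients, a two-sided 5% paired t-test has 80% power for a mean within-patient treated-minus-vehicle PAHPI difference, at a named visit such as week 12, of 0.58 SD of the within-patient differences (0.63 SD with 22 completers, 0.66 SD with 20).*

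Say whether the quantity compared is the score at that visit or its change from baseline. Label the completer numbers, and any SD used to convert to PAHPI points, as assumptions.

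If a comparison of proportions is kept, define response on the PAHPI, name a paired test, and state the assumed side rates and discordance with the resulting power.

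The cost is one rewritten paragraph, with no extra patients and no change in conduct. The claim changes from an unconditional 30% to a detectable difference in SD units.
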